4.8.4 Haematology, Clinical Chemistry and Renal Function Parameters

The following haematology and clinical chemistry (including renal function) parameters will be summarised.

Category	Parameter	Unit
Haematology	Haemoglobin	g/L
	Haematocrit	L/L

CONFIDENTIAL

Sponsor:	Zambon S.p.A.	Protocol Number:	Z7224L02
----------	---------------	------------------	----------

	Red Cell Count	x10E12/L
	White Cell Count	x10E9/L
	Neutrophils	%
	Total Lymphocytes	%
	Monocytes	%
	Eosinophils	%
	Basophils	%
	Neutrophils (Abs)	x10E9/L
	Total Lymphs (Abs)	x10E9/L
	Monocytes (Abs)	x10E9/L
	Eosinophils (Abs)	x10E9/L
	Basophils (Abs)	x10E9/L
	Platelets	x10E9/L
Chemistry	Sodium	mmol/L
	Potassium	mmol/L
	Chloride	mmol/L
	Uric Acid	mmol/L
	Bilirubin (Total)	umol/L
	Bilirubin (Conj)	umol/L
	AST	U/L
	ALT	U/L
	GGT	U/L
	ALP (Alk Phos)	U/L
	Calcium	mmol/L
	Amylase	U/L
Renal Function	BUN (Urea)	mmol/L
	Creatinine	umol/L

Results as assessed at each applicable visit will be summarised by treatment group and overall using descriptive statistics for continuous variables. Absolute and percentage changes from baseline will also be presented.

A shift table will also be provided presenting results as lower than, within and higher than the central laboratory normal range. This will show the shift from baseline to each post-baseline visit, as well as to the most extreme value (defined as the value furthest outside [below or above] the central laboratory normal range) at any visit after baseline, including unscheduled visits.

Notes:

- Change from baseline for each parameter will be computed using the formula:

$$\text{Change (unit)} = (\text{AVAL [unit]} - \text{baseline AVAL [unit]});$$

- All results outside the central laboratory normal range will be flagged in the data listings;

CONFIDENTIAL

Sponsor:	Zambon S.p.A.	Protocol Number:	Z7224L02
----------	---------------	------------------	----------

- Repeat laboratory results within a visit will replace the original value;
- Due to CTP amendments and to the corresponding changes in the procedures schedule and due to differences in the schedule of assessments in the local versions of the CTP, not all the subjects have undergone the same sequence of laboratory assessments. All the values collected will be summarised jointly. Considering the presence of a stratified and permuted blocks randomisation list, no imbalance between treatments is expected.

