4.1. EVALUATION OF THE ANTICIPATED RISKS AND BENEFITS

Colistimethate sodium (commercially available as Promixin®/Tadim®) is indicated for the management of chronic pulmonary infections due to *P. aeruginosa* in adult and paediatric patients with CF. Colistimethate sodium has a well-established safety profile in subjects with CF (Promixin Summary of Product Characteristics [SmPC], [16]). Patient exposure data for CF patients in key European markets using commercial colistimethate sodium drug product (Promixin®/Tadim®) delivered with the CCI nebulizer estimates the number of treatment days as 13,146,075 (March 2003 to 31st July 2017, inclusive), with a low level of spontaneous adverse drug reactions reported.

Common side-effects of nebulisation include coughing and bronchospasm with the first administration, observed in approximately 10% of subjects. Other common side-effects on the respiratory system include chest tightness and bronchoconstriction. During the trial, subjects will administer a bronchodilator (salbutamol/albuterol) provided by the Sponsor prior to each administration in order to reduce the side-effects described above. If subjects prefer not to use the bronchodilator, and the Investigator confirms that the subject can tolerate IMP without it, this is acceptable provided this is documented accordingly. To monitor subjects for bronchial hyperreactivity in response to colistimethate sodium which may develop with continued use, regular spirometric examinations are included in the trial schedule. Further side-effects observed include hypersensitivity reactions such as skin rash and cases of sore throat or sore mouth (also potentially due to superinfection with *Candida* species).

High serum concentrations may lead to a reduction of pre-synaptic acetylcholine release and thus may prolong the effects of muscle relaxants and increase fatigue. In addition, high serum concentration may result in renal impairment; whilst this is highly unlikely during inhalation therapy, in the current protocol an evaluation of renal function will be performed at baseline and during treatment.

Colistimethate sodium should be used with extreme caution in subjects with porphyria.

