10.1.4. LABORATORY EVALUATIONS

Routine laboratory evaluations will be performed at the Screening Visit (Visit 1), Visit 5, and Visit 7. The haematology and clinical chemistry parameters detailed in Table 1 will be analysed at the central laboratory using standard, validated laboratory methods.

Renal function will be monitored by laboratory tests (creatinine, Blood Urea Nitrogen [BUN]) performed at the Screening Visit (Visit 1) and during the treatment: at Day 28 of treatment (Visit 3), after 6 months (Visit 5), and at the end of treatment (Visit 7).

Subjects with clinically relevant impaired renal function (as defined by serum creatinine levels $\geq 2.0x$ upper limit of normal) will be discontinued.

Note that at Visit 1 and Visit 7 the blood samples for these assessments must be collected after the 12-lead ECG assessments have been performed.

A dipstick urine pregnancy test for women of child-bearing potential will be performed at the investigational site at the Screening Visit (Visit 1) and at all scheduled study visits thereafter.

Female subjects who become pregnant during the trial must be withdrawn from the trial without delay and will be followed up to determine the outcome of the pregnancy. The Investigator is required to inform the Sponsor of a subject's pregnancy and the estimated date of delivery. Reporting requirements are outlined in [Section 17.10](#).

Clinical laboratory tests will be reviewed for results of potential clinical significance before Visit 2 to confirm patient's eligibility and during the trial, as appropriate.

Clinically significant laboratory abnormalities arising from Visit 2 onwards are considered to be AEs. Where possible, a diagnosis should be ascribed to the abnormal lab test.

Table 1 CLINICAL LABORATORY EVALUATIONS

Haematology: at the Screening Visit (Visit 1), Visit 5, and Visit 7			
Haematocrit	Haemoglobin	Platelet count	Red blood cell count
White blood cell count and differential (neutrophils, lymphocytes, monocytes, eosinophils and basophils)			
Clinical Chemistry: at the Screening Visit (Visit 1), Visit 5, and Visit 7			
BUN*	Chloride		AST
Creatinine*	Uric acid		ALT
Sodium	Amylase		GGT
Potassium	ALP		Bilirubin (direct and total)
Calcium			
Pregnancy Test (women of child-bearing potential only):			
Urine β -hCG (dipstick) at the Screening Visit (Visit 1) and at all visits thereafter			
* These evaluations will also be performed at Visit 3			

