4.1.11 Exclusion of Data from the Statistical Analysis

If a subject received the incorrect treatment after being treated with the correct one, all the data collected after the date of the wrong treatment dispensing will be reported in listings and flagged, but not included in the statistical analysis on the ITT, mITT, Safety and PP populations.

Unless stated otherwise, primary efficacy endpoint and related assessments conducted at an early termination visit or unscheduled visit will be included in the statistical analysis, Where not stated differently, other assessments conducted at an early termination visit and unscheduled assessments will not be considered in the statistical analysis, but will be listed only.

Only NCFB pulmonary exacerbations with a start date \geq date of first IMP dose and \leq date of treatment completion/discontinuation will be considered in the analysis.

In case of data excluded from the statistical analysis (in the situations described above but also in other cases, for example: spirometry tests excluded due to technical issues, or assessment not done), the derived variables based on these data will not be calculated. For example, the change from baseline to Visit 5 will not be calculated if the measurement at Visit 5 is excluded from the statistical analysis, or all the changes from baseline will not be calculated if the measurements pre-dose are excluded.

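### The worst-value laboratory shift keeps only one side per subject, and no table listed in the SAP counts creatinine at or above the protocol's 2.0 x ULN limit by arm

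*SAP*

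**What the plan says.** SAP 4.8.4 plans descriptive statistics, changes from baseline and a three-class shift table for every haematology, chemistry and renal parameter: "A shift table will also be provided presenting results as lower than, within and higher than the central laboratory normal range". On the by-visit part it says: "This will show the shift from baseline to each post-baseline visit". The same table also has a shift to the most extreme value, "defined as the value furthest outside [below or above] the central laboratory normal range", taken "at any visit after baseline, including unscheduled visits". The SAP does not state the scale on which furthest is judged, and it plans no separate shifts to the lowest and the highest value.

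SAP 4.1.11 sets the default for results off the visit schedule. Where no section provides for something else, "other assessments conducted at an early termination visit and unscheduled assessments will not be considered in the statistical analysis, but will be listed only".

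On renal function, Protocol 4.1 notes that "high serum concentration may result in renal impairment". It regards this as very unlikely with inhalation, and adds that "in the current protocol an evaluation of renal function will be performed at baseline and during treatment". The rule in Protocol 10.1.4 begins "Subjects with clinically relevant impaired renal function (as defined by serum creatinine levels"; the limit it then gives is 2.0 x ULN, and such subjects are to be discontinued. Exclusion criterion 18 uses the same limit. The chemistry outputs in SAP 5.3.4 are a results-and-change table (14.3.4.5.2.1) and a shift table (14.3.4.5.2.2).

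**The concern.** Two separate weaknesses meet in this table.

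First, high and low values compete for one cell. For vital signs, physical examination and ECG (SAP 4.8.5 to 4.8.7) a single worst result is well defined, because normal, abnormal NCS and abnormal CS are ordered. A laboratory value can be abnormal in two directions. Keeping one direction discards the other, and with the distance scale unstated two programmers could classify the same subject differently. The rule covers every parameter in 4.8.4, including those where both directions matter, such as potassium, sodium, calcium and white cells.

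Second, the three classes do not separate a trivial rise in creatinine from one that meets the protocol's own definition of clinically relevant renal impairment. The protocol monitors renal function for a named risk, but the planned summary does not use the protocol's criterion. By contrast, SAP 4.8.2 counts the >15% FEV1 fall by arm at Visit 7, with confidence intervals, a relative risk and a Fisher test; that fall is also tied to a withdrawal rule.

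At stake is whether the safety tables can show, or rule out, a difference between arms in subjects reaching the renal limit, and whether the only by-arm summary stated to include unscheduled results shows both directions.

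**Working it through.** The documents give no figure to reproduce: this is a descriptive rule. The check asks which values the rule can drop and which outputs remain.

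**Inputs.** The selection rule and its scope are from SAP 4.8.4, the default for unscheduled results from SAP 4.1.11, and the 2.0 x ULN limit from Protocol 10.1.4. The documents give no creatinine reference range, so 45-84 umol/L is assumed, with assumed ranges from 40-80 to 64-104 as a check.

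**When a raised value is displaced.** Let L and U be the lower and upper limits, x a low value and h a high value in the same subject. The low value is kept when:

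- absolute scale: L - x > h - U, that is h < U + (L - x)
- relative scale: (L - x)/L > (h - U)/U, that is h/U < 2 - x/L
- log scale: ln(L/x) > ln(h/U), that is h/U < L/x

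With L = 45, U = 84 and x = 30, raised values are displaced below:

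- absolute: 84 + 15 = 99 umol/L, or 99/84 = 1.18 x ULN
- relative: 2 - 30/45 = 1.33 x ULN, or 112 umol/L
- log: 45/30 = 1.50 x ULN, or 126 umol/L

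A subject with 95 and 30 is therefore tabulated as lower on all three scales (absolute distances: 95 - 84 = 11 above, 45 - 30 = 15 below). A subject with 105 and 30 is higher on the absolute scale (21 against 15) but lower on the relative scale (0.25 against 0.33) and on the log scale (ratio 1.25 against 1.50). The unstated scale decides the class.

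For a low value of 0.7 x LLN across the assumed ranges, the cut-offs are 1 + 0.3 L/U = 1.15 to 1.18 x ULN (absolute), 2 - 0.7 = 1.30 x ULN (relative) and 1/0.7 = 1.43 x ULN (log).

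**Upper bound on the loss.** Take h at or above 2U.

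- Absolute: h - U is at least U, while L - x is at most L, and L < U. The high value always wins. Even with x going to 0, nothing above 84 + 45 = 129 umol/L (1.54 x ULN) is displaced.
- Relative: (h - U)/U is at least 1, while (L - x)/L is below 1 for any positive x. The high value always wins.
- Log: displacement would need x below L/2, here 22.5 umol/L.

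**Where a displaced value can still be seen.** At a scheduled visit it appears in the by-visit shift. At an unscheduled visit, SAP 4.1.11 leaves it to the listings, and the most-extreme column is the only by-arm laboratory summary stated to include it. Early-termination values are unclear: SAP 4.1.10 allocates that visit to Visit 7 in the analysis datasets, while 4.1.11 would only list such assessments.

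**Merging at the renal limit.** With U = 84, a creatinine of 1.05 x 84 = 88.2 and one of 2.0 x 84 = 168 umol/L both fall in the higher class, and neither table in SAP 5.3.4 separates them. For scale only: 287 subjects were randomised (SAP 3.9), about 287/2 = 143.5 per arm. If 1% to 2% reached the limit (an assumption), that is 1.4 to 2.9, or about 1 to 3 subjects per arm, within a class that also holds every mild rise.

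**The case against.** The case for leaving the table alone has several sound parts. Displacement needs one subject to be above range at one visit and below it at another, which for creatinine is an unusual swing. By-visit shifts are shown in full, and Protocol 19.4.3 also promises out-of-range frequencies by visit and arm. Under Protocol 10.1.4, clinically significant laboratory abnormalities from Visit 2 onwards are adverse events, so they reach the TEAE tables by arm. A subject discontinued at the limit could appear in the table of TEAEs leading to permanent discontinuation (14.3.1.2.5) or among withdrawal reasons. The by-visit descriptive statistics include the maximum, and listings flag out-of-range values. The protocol itself thinks renal impairment very unlikely by this route and names no adverse events of special interest. Nothing here is inferential or favours one arm.

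Most of this stands and limits the weight of the point, but it does not supply the missing count. The adverse event route depends on investigator judgement and coding, not on the measured value. A maximum shows one value per arm and visit, not how many subjects reached the limit. Listings give no comparison by arm.

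A reader might also infer that unscheduled visits are where suspected renal problems are checked. The documents do not say so. Renal tests are scheduled at Visits 1, 3, 5 and 7 (the French schedule adds Visits 4 and 6), and SAP 4.8.4 lets a repeat within a visit replace the original, so a re-check need not be an unscheduled record. Unscheduled results matter here only because of how SAP 4.1.11 treats them.

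**Conclusion.** The point holds as two independent reporting gaps of modest size.

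The single two-sided extreme can place a subject on one side only and drop a mildly raised value. With the assumed 45-84 range and a low value of 30, the cut-off is 1.18 x ULN on the absolute scale and 1.33 x ULN on the relative scale. The consequence is greatest for unscheduled results and extends to every parameter with two meaningful directions.

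It would be tempting to conclude that a marked creatinine rise could vanish from the table. That does not follow: on an absolute or relative scale a value at or above 2 x ULN cannot be displaced, and on a log scale it would take a low value under half the LLN. For such values the problem is merging, not loss. They are shown as higher, together with values just above ULN, and no output in the SAP table list counts them by arm. Of the two gaps, this missing count is the more consequential.

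The reference ranges and the 1% to 2% are assumptions, and the frequency of affected subjects is not in the documents. The statement about missing counts covers the SAP text and its table list; the separate table shells were not available.

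**What to change.** In SAP 4.8.4, replace the single most-extreme shift by two: baseline to the lowest and baseline to the highest post-baseline value, both including unscheduled visits. No distance scale is then needed.

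In the creatinine table, add the number and percentage of subjects per arm with any post-baseline value at or above 2.0 x ULN. State that unscheduled and early-termination values are included, since SAP 4.1.10 and 4.1.11 point in different directions on the latter.

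The cost is a change of SAP wording, one more column in each laboratory shift table and one more row for creatinine. It uses data already collected and a threshold the protocol already contains, and it leaves every clinical rule as it is.

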4.1.12 Listings

All data collected will be presented in the listings.

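### Same-visit repeat laboratory results replace the original unconditionally, so a valid out-of-range value can drop out of the SAP's most-extreme-value shift

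*SAP*

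**What the plan says.** SAP 4.8.4 plans a laboratory shift table "presenting results as lower than, within and higher than the central laboratory normal range". It shows the shift from baseline to each post-baseline visit and also to the most extreme result, "defined as the value furthest outside [below or above] the central laboratory normal range", taken "at any visit after baseline, including unscheduled visits".

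The notes to the same section add the rule "Repeat laboratory results within a visit will replace the original value". It has no condition on why the test was repeated and no exception for any table.

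Two other provisions keep the replaced result visible. SAP 4.1.12 says "All data collected will be presented in the listings", and SAP 4.8.4 says "All results outside the central laboratory normal range will be flagged in the data listings". Protocol 10.1.4 also treats laboratory abnormalities of clinical significance arising from Visit 2 onwards as adverse events.

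**The concern.** A most-extreme-value column exists to catch excursions that by-visit summaries can miss. An unconditional replacement rule works against that purpose: it discards a valid first result in favour of a second one taken at the same visit, and the column then takes its extreme from what is left.

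What is at stake is the accuracy of one descriptive safety table. That table carries some weight. Protocol 19.4.3 promises by-visit frequencies of out-of-range values by treatment group. The SAP's table list (5.3.4) has only results-and-change tables and shift tables for haematology and clinical chemistry. The shift table is therefore the only planned comparison of out-of-range laboratory values between arms, and the replacement rule acts on it. Renal function is monitored on purpose in this trial (Protocol 4.1 and 10.1.4), so creatinine and BUN are analytes for which the column will be read.

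**Working it through.** The plan gives no figure to reproduce, so the check applies the rule and then the definition of the extreme value.

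**Inputs**
- Replacement rule, extreme-value definition and low/within/high categories: SAP 4.8.4.
- Laboratory baseline is Visit 1: SAP 4.1.6.
- Scheduled post-baseline values under the global schedule (Protocol 10.1.4): Visits 5 and 7 for haematology and chemistry, so 2 values; Visits 3, 5 and 7 for creatinine and BUN, so 3 values.
- Exceptions: none was found in SAP 4.1.6, 4.1.11, 4.1.12, 4.8.4 or 4.11, nor in Protocol 10.1.4 or 19.4.3.

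**Direction.** Let L and U be the limits of the normal range, and let the distance of a value v outside it be D(v) = max(0, L − v, v − U). Write E(all) for the largest D over all valid post-baseline results and E(rule) for the largest D after replacement. Taking repeats as valid, the results kept under the rule are a subset of all valid results, so E(rule) ≤ E(all). A repeat more extreme than the original is counted either way. For the post-baseline extreme, the rule can only lower the result or leave it unchanged.

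**Cases** (hypothetical; baseline within range, other post-baseline values within range unless stated)

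| Case | Category under the rule | Category from all valid results |
|---|---|---|
| Visit 5 high, same-visit repeat within | within | high |
| Visit 5 high, same-visit repeat high but less so | high (smaller value) | high |
| Visit 5 high, same-visit repeat higher | high | high |
| Visit 5 high, same-visit repeat within, Visit 7 high | high | high |
| Visit 5 high, repeat within at a separate unscheduled visit | high | high |
| Visit 5 high but sample invalid, repeat within | within | within |

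Only the first row gives a wrong category. It needs a valid original, a repeat logged to the same visit that is back in range, and no other post-baseline value placing the subject in that category. (A subject with values out of range on both sides could also move between low and high.) With only 2 or 3 scheduled post-baseline values, one replacement can decide the category.

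**Baseline.** The rule also covers Visit 1. If a high baseline is replaced by an in-range repeat, a later high value is shown as within-to-high instead of high-to-high. That error runs the other way and overstates a shift.

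**Comparison within the SAP.** The worst-result shifts for vital signs (4.8.5), physical examination (4.8.6) and ECG (4.8.7) carry no replacement rule.

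**The case against.** The strongest reply is that little is lost. The original stays in the listings with its out-of-range flag, and an abnormality judged clinically significant is an adverse event and enters the adverse event tables. A reader might infer that a raised creatinine followed by a normal repeat would be reported as normal everywhere; the documents do not support that. The loss is confined to the shift table and the by-visit summaries. This stands, with one limit: listings do not compare arms, and the adverse event route captures only what the investigator judges significant.

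A second reply concerns renal safety. Protocol 10.1.4 requires discontinuation of "Subjects with clinically relevant impaired renal function", defined by a serum creatinine threshold. It is tempting to conclude that the rule could hide such an event. It does not follow: nothing links that action to the value kept in the analysis dataset, reasons for withdrawal are tabulated separately (SAP 4.3), and a low/within/high table does not display the threshold. This stands in full.

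Third, the documents do not say what triggers a repeat. That repeats usually follow an abnormal first result is an assumption. Samples go to a central laboratory, so a confirmatory draw may well fall at an unscheduled visit, where both values remain eligible. That is also inference, because the documents do not say how such draws are labelled. The point stands as a limit on frequency; it does not remove the inconsistency.

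Finally, replacing a spoiled sample is sensible. Agreed, but the rule is not limited to spoiled samples.

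**Conclusion.** The point holds as an internal inconsistency in SAP 4.8.4: the extreme-value column is defined over all post-baseline visits, yet an unconditional rule removes valid results before the extreme is taken. The direction is fixed for the post-baseline extreme only, and it assumes that the retained repeats are themselves valid.

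The number of subjects affected cannot be estimated and could be zero, since no repeat rate or trigger is given. A reader might go further and say that the safety table is biased towards no treatment effect. The documents do not show that: the rule applies alike to both arms under blinding, a repeated Visit 1 result can push the shift the other way, and the laboratory outputs are descriptive with no test or decision attached.

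Severity is minor. The issue is the accuracy of safety reporting; it does not touch efficacy, alpha, adverse event reporting or the monitoring of patients.

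**What to change.** In SAP 4.8.4, state that the shift to the most extreme post-baseline value, and any out-of-range counts, use all valid results, both original and repeat, and leave out only originals documented as invalid. The replacement rule may stay for by-visit summary statistics, where it is a matter of convention.

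The cost is one sentence and one programming condition, with no new data collection beyond a record of why an original was invalid, if none exists. The table will show slightly more transient out-of-range values. If the blind has already been broken, the revised derivation can be given as an additional table labelled post hoc, in line with SAP section 1.
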